5.2.2 Missing Data Handling- A While-on-Treatment Strategy

If, on the week of interest, for both primary and secondary endpoints, data is missing for more than 5 subjects due to permanent premature treatment discontinuation, then imputation will be performed using the missing data imputation approach and by disregarding any available data for those subjects.

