8.8.1 Primary endpoint

The primary endpoint, mean change in weekly mean WI-NRS recorded in the subject's diary from Baseline to Week 12 for MC2-25 cream compared to MC2-25 vehicle, will be analysed by a mixed model of repeated measures with Baseline weekly mean WI-NRS as covariate and treatment, CKD stage stratum at baseline, systemic CKP-aP treatment status at baseline and visit as fixed factors with a two-sided α =0.05. The weekly mean WI-NRS is calculated as the average of minimum 4 WI-NRS values recorded once daily in the subject's diary from 7 days prior to and including the visit days (i.e., must be recorded for 8 days total).

On the FAS, the primary analysis and one sensitivity analysis will follow a treatment policy strategy irrespective of any potential intercurrent events. On primary analysis, missing values will be replaced following a multiple imputation procedure adequate for the endpoint assuming missingness appearing at random and based on 20 imputations. On the FAS, sensitivity analyses will include imputation by last observation carried forward (LOCF; treatment policy strategy) and multiple imputation of missing data and all data after start of rescue medication (hypothetical strategy).

Applying the same statistical model, further estimands include multiple imputation on the MFAS and as observed on the PPS, both following a treatment policy strategy. If deaths occur, further estimands may be defined following a composite endpoint strategy.

Supportive subgroup analyses will be conducted by dialysis status and CKD stages and by country on the FAS.

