5.2 Handling of Dropouts or Missing Data

5.2.1 Missing Data

For the primary and secondary efficacy endpoints, the primary estimands using the FAS, MFAS and PPS will use a treatment policy strategy for missing data. Missing data will be replaced using a multiple imputation (MI) approach. Note, missing data includes dropouts, empty data fields after dropout date will be handled as missing data regardless of reason for drop out. MI will be performed for all populations separately only if there is a difference in populations. Seed numbers for each endpoint will use the randomly generated 4-digit numbers from the table below. Other variables that are included in the imputation model will include treatment, site, country, visit, and key baseline characteristics such as age, gender, race, CKD stage stratum⁽¹⁾ at baseline, and systemic CKD-aP treatment status⁽²⁾ at baseline. Depending on the pattern of missingness, a 2-step process may be employed. If missing data points occur for an intermediate visit, they will be imputed first using a Markov Chain Monte Carlo (MCMC) method. As a result, a monotone missingness pattern will be obtained for the data to be fully imputed. The subsequent imputation will use general regression for continuous variables and logistic regression for categorical variables under the assumption data are missing at random to produce 20 imputed datasets where the remaining missing data are filled in using 20 separate sets of values. For the categorical secondary variables, the percentages will be calculated from the above imputed data.

- (1) CKD stage stratum at baseline= A. ≥40% of subjects must be on dialysis (HD or HDF) and must be CKD stages 4-5 (CKD stage 4-5 dialysis) B. ≥20% of subjects must Not be on dialysis and must be CKD stages 4-5 (CKD stage 4-5 non-dialysis) C. ≥20% of subjects must Not be on dialysis and must be CKD stage 3 (CKD stage 3)
- (2) Systemic CKD-aP treatment status at baseline will be flagged as "Yes" if prior/concomitant medication falls within one of the ATC groups provided in Section 6.3.2

Table 9 Population and Random Seed Number

Population	Random Seed Number
FAS	6529
MFAS	7631
PPS	9376

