For each copy of the imputed datasets, both the primary and secondary endpoints involving the same endpoint variable will be analyzed in the same way as described in the primary and secondary analyses in Sections 5.5.1 and 5.5.2, respectively. Results from the copies of the imputed datasets will be synthesized using SAS[®] Proc MIANALYZE.

Using the FAS for the primary endpoint analyses, a sensitivity analysis will be performed using last observation carried forward (LOCF; treatment policy). If a subject is given prohibited therapy, all missing data and data for visits after the start of prohibited therapy will use the MI approach described above in another analysis (hypothetical strategy).

If deaths occur, further estimands may be defined following a composite endpoint strategy.

There will be no imputation of missing data for the PPS which will use the data as observed following a treatment policy strategy. There will be no imputation of missing data for safety endpoints.

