5.2.3 Analysis Windows

As subjects do not always adhere to the protocol visit schedule, the following rules are applied to assign actual visits to analysis visits. Listed below are the visit windows and the target days for each visit. The reference day is Baseline, Study day 1. If a subject has 2 or more actual visits in 1 visit window, the visit closest to the target day will be used as the protocol visit for that visit window. The other additional visit(s) will not be used in the summaries or analyses, but they can be used for determination of clinically important endpoints. If 2 actual visits are equidistant from the target day within a visit window, the later visit is used.

Table 10 represents the analysis windows assigned for efficacy and safety analysis and the corresponding range of treatment days (window) during which data for a particular nominal visit will be collected. The analysis windows will be calculated from the first application of study product. These are analysis windows that contain, but are not same as, the actual visit windows.

For assessments that are not planned on Week 1, the visit window for such assessments will be starting at Week 4.

Study Week/ Period	Study Visit	Target Day	Window
Screening	Visit 1 (V1)	-28 to -1	
Baseline/ Week 0 (on site)	Visit 2 (V2)	1	1
Week 1 (on site)	Visit 3 (V3)	8 (±1)	2-19
Week 4 (on site)	Visit 5 (V5)	29 (±4)	20-43
Week 8 (on site)	Visit 7 (V7)	57 (±4)	44-71
Week 12 (on site/EoT)	Visit 9 (V9)	85 (±4)	72-92
Week 14 (FU)	Visit 10 (V10)	±2 Weeks after EoT	

Table 10Study Period, Visit and Target Day

For the hypothetical strategy, subjects given prohibited therapies will have WI-NRS data set to missing for visits after the start of the prohibited therapies and then missing data will be estimated using MIs. Subjects with an ET visit will be excluded from the PPS analyses. Safety data collected during an ET visit will remain at the Week 12/EoT visit.

Note: As per the CDISC, baseline is defined as Day 1 and not as Day 0. Therefore, there is a difference of one day between study day as defined in protocol and target day (Table 10).

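### SAP 5.2.2 is headed a while-on-treatment strategy, but it imputes the week of interest, puts no time limit on the data it discards, and runs only if a count exceeds 5

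*SAP*

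**What the plan says.** SAP 5.2.2 is a single conditional sentence covering the primary and secondary endpoints. The condition is that, at the week of interest, "data is missing for more than 5 subjects due to permanent premature treatment discontinuation". The action is that "imputation will be performed using the missing data imputation approach and by disregarding any available data for those subjects". The section does not say whether the analysis is primary, sensitivity or supplementary, and it does not say which of a subject's data are meant.

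The surrounding text is more specific:

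- SAP 5.2.1 says that "the primary estimands using the FAS, MFAS and PPS will use a treatment policy strategy for missing data" and describes multiple imputation "under the assumption data are missing at random", with 20 imputed datasets. It labels LOCF a sensitivity analysis and the hypothetical strategy another analysis.
- SAP 5.2.3 gives the hypothetical strategy a clear limit: "subjects given prohibited therapies will have WI-NRS data set to missing for visits after the start of the prohibited therapies".
- Protocol 8.8.1 says that "the primary analysis and one sensitivity analysis will follow a treatment policy strategy irrespective of any potential intercurrent events". It goes on to list LOCF, hypothetical, MFAS, per-protocol and possible composite analyses, but no while-on-treatment analysis.
- SAP 5.5.1 and 5.5.2 do not refer to 5.2.2, and the table of changes in SAP 6.2 does not list it.

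**The concern.** In standard estimand terms (the documents do not define the label), a while-on-treatment strategy takes the response observed up to discontinuation as the outcome of interest. Nothing after that point needs to be imputed. SAP 5.2.2 does the reverse: it fills in a value at the week of interest and sets observed data aside. A result reported under that heading would carry the wrong estimand label.

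The scope of the deletion matters too. For a subject who stopped treatment after Week 4, the Week 1 and Week 4 diary means are on-treatment data. So may be part of an early EoT assessment, which SAP 5.1 assigns to the nearest scheduled visit. These are the observations that make a missing-at-random imputation plausible for that subject. If they are discarded, the imputed value rests on treatment arm and baseline characteristics alone, and any link between early poor response and stopping is lost.

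Finally, whether the analysis exists at all depends on a count seen in the data, with no reason given for the number 5.

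**Working it through.** **1. Heading against method.** The heading promises response up to discontinuation. The text delivers an imputed value at the week of interest, using the only imputation approach in the SAP (5.2.1, missing at random). If post-discontinuation values were removed and the target week imputed from earlier data, the quantity estimated would be the response had treatment continued. That is a hypothetical strategy.

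**2. Which data are disregarded?** Three readings are possible.

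- *Only the week of interest.* The subjects concerned are by definition already missing at that week. Under SAP 3.1 the weekly mean is missing when fewer than 4 of the 8 diary entries exist, so at most 3 entries, or an on-site score, are left to disregard. The instruction would be almost empty.
- *Only values after discontinuation.* This would be a sensible rule, but the text does not state it. SAP 5.2.3 shows that the authors write such a limit when they intend one.
- *All available data.* This is the literal reading. It removes on-treatment WI-NRS values.

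**3. Who is covered?** The rule applies to discontinuers whose data are missing. Protocol 5.4 encourages subjects who stop treatment to keep attending. Those who do so have Week 12 data, and the rule does not clearly reach them. Taken literally, off-treatment Week 12 values of attenders stay in while on-treatment values of non-attenders go out, which is the opposite of what the heading implies.

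**4. How often would the rule fire?** SAP 5.2.2 gives no computed figure to reproduce. The inputs are:

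- N = 108 and 10% dropout, both from Protocol 8.2.
- The threshold of more than 5, from SAP 5.2.2.
- The rate p of Week 12 data missing because of treatment discontinuation. The documents do not give it, so p is an assumption and a range is shown.

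With the count X taken over all randomised subjects,

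P(X > 5) = 1 − Σ (k = 0 to 5) C(108, k) p^k (1 − p)^(108 − k).

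| Assumed p | Expected count 108 × p | P(X > 5) |
|---|---|---|
| 10% | 10.8 | 0.965 |
| 7.5% | 8.1 | 0.828 |
| 5% | 5.4 | 0.456 |
| 3% | 3.2 | 0.107 |
| 2% | 2.2 | 0.022 |

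The 10% row treats every planned dropout as a permanent treatment discontinuation with missing Week 12 data, so it is an upper bound at the planned rate. If half of the planned 10% qualify, p is 5% and the chance is 46%. If 30% qualify, p is 3% and the chance is 11%. Over this range, whether the analysis is run goes from unlikely to near certain.

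**The case against.** The strongest reply is that nothing of consequence depends on this section. Protocol 8.8.1 and SAP 5.2.1 fix treatment policy for the primary analysis and SAP 5.5.1 does not invoke 5.2.2, so its role as a supplementary analysis can be inferred. That is right. A reader might infer that 5.2.2 overrides the primary analysis once the count passes 5. The documents do not support this, because it would contradict two explicit statements. What remains is that the SAP labels its other alternative analyses and leaves this one unlabelled.

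A second reply is that the fully literal reading cannot be executed: discarding everything would also remove the baseline values that the imputation model and the MMRM need, so the authors must have meant less. This has force, and off-treatment values may well be what they had in mind. But the text does not say where the line falls, and a programmer could keep baseline and still drop every post-baseline value.

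A third reply is that the threshold is pre-specified, can be checked on blinded pooled counts, and spares a run when few subjects are affected in an exploratory phase 2 trial. That is fair as far as it goes. Running the analysis regardless is the better convention, and the trigger alone would not justify a change.

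A reader might also make much of whether the 5 are counted per arm. The plain reading is a pooled count, since the SAP says by treatment group where it means that. Per-arm figures therefore add little.

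**Conclusion.** The point holds for a supplementary analysis. As written, SAP 5.2.2 is not a while-on-treatment analysis, and its instruction to disregard data has no stated limit and can be read to remove on-treatment WI-NRS values. These two defects follow from the text and need no assumption beyond the standard meaning of the label. The trigger is a lesser matter: about 96% likely to be met at the planned dropout if all dropouts count, and 46% at 5%, on a pooled count and an assumed rate. The missing role label and the omission from SAP 6.2 are points of clarification.

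A reader might go further and infer that the trial's treatment effect is biased by some known amount. The documents do not support that. The primary treatment-policy analysis does not use this rule on the natural reading. A shift in the supplementary estimate would need the broader deletion together with stopping that depends on response and differs between arms. The documents give neither stopping rates by arm nor correlations between visits, so the size of any such shift is not established. If only post-discontinuation values are discarded, this loss of on-treatment information does not occur.

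**What to change.** Amend SAP 5.2.2 before database lock:

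1. State that it is supplementary to the primary treatment-policy analysis.
2. Delete the condition on more than 5 subjects and run the analysis unconditionally.
3. Replace the instruction to disregard available data with a rule that sets only WI-NRS values after permanent treatment discontinuation to missing. Apply it to all discontinuers, including those who keep attending, and keep baseline and on-treatment values in the imputation model.
4. Make heading and method agree. Either call it a hypothetical strategy, or define a true while-on-treatment endpoint (response up to discontinuation) with no imputation of the week of interest. In the second case the imputation wording goes.
5. List the analysis in SAP 6.2 as an addition to Protocol 8.8.1.

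The cost is SAP wording only. There is no change to data collection, sample size or the primary analysis. The one downside is an extra supplementary run even when few subjects discontinue.

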5.2.3 Analysis Windows

As subjects do not always adhere to the protocol visit schedule, the following rules are applied to assign actual visits to analysis visits. Listed below are the visit windows and the target days for each visit. The reference day is Baseline, Study day 1. If a subject has 2 or more actual visits in 1 visit window, the visit closest to the target day will be used as the protocol visit for that visit window. The other additional visit(s) will not be used in the summaries or analyses, but they can be used for determination of clinically important endpoints. If 2 actual visits are equidistant from the target day within a visit window, the later visit is used.

Table 10 represents the analysis windows assigned for efficacy and safety analysis and the corresponding range of treatment days (window) during which data for a particular nominal visit will be collected. The analysis windows will be calculated from the first application of study product. These are analysis windows that contain, but are not same as, the actual visit windows.

For assessments that are not planned on Week 1, the visit window for such assessments will be starting at Week 4.

Study Week/ Period	Study Visit	Target Day	Window
Screening	Visit 1 (V1)	-28 to -1	
Baseline/ Week 0 (on site)	Visit 2 (V2)	1	1
Week 1 (on site)	Visit 3 (V3)	8 (±1)	2-19
Week 4 (on site)	Visit 5 (V5)	29 (±4)	20-43
Week 8 (on site)	Visit 7 (V7)	57 (±4)	44-71
Week 12 (on site/EoT)	Visit 9 (V9)	85 (±4)	72-92
Week 14 (FU)	Visit 10 (V10)	±2 Weeks after EoT	

Table 10Study Period, Visit and Target Day

For the hypothetical strategy, subjects given prohibited therapies will have WI-NRS data set to missing for visits after the start of the prohibited therapies and then missing data will be estimated using MIs. Subjects with an ET visit will be excluded from the PPS analyses. Safety data collected during an ET visit will remain at the Week 12/EoT visit.

Note: As per the CDISC, baseline is defined as Day 1 and not as Day 0. Therefore, there is a difference of one day between study day as defined in protocol and target day (Table 10).

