Diary (Handout)	Х	Х	Х		Х		Х			
Biopsy ¹⁵		Х							Х	
Tape stripping ¹⁶		Х							Х	
Prior & concomitant therapies ¹⁷	Х	Х	Х	Х	Х	Х	Х	Х	Х	Х
Adverse events		Х	Х	Х	Х	Х	Х	Х	Х	Х
Investigational medicinal product (IMP) dispensation		Х			Х		Х			
IMP return, compliance and accountability					Х		Х		Х	
IMP application ¹⁸				_	Х					
Diary (Review)		Х	Х		Х		Х		X	

- 1. Follow-up (FU) visit is only applicable if there are ongoing serious adverse events (SAEs) or related adverse events (AEs) at Week 12. (X) indicates assessments to be performed if judged necessary by the investigator.
- 2. An unscheduled visit can be conducted to perform any of the postbaseline assessments or procedures included in the SoA if deemed necessary by the Investigator.
- 3. In the case of trial withdrawal or treatment discontinuation, all assessments of the Week 12 (End of Treatment [EoT]) visit have to be performed. The end of treatment form must be completed when treatment is discontinued and the end of trial form must be completed at end of the trial or in case of trial withdrawal.
- 4. Phone calls: To remind subjects about diary documentation (in particular once-daily WI-NRS assessments that must be performed for 8 days leading up to each on-site visit [i.e., from day -7 to day 0 where day 0 = next on-site visit day]) and to ask for AEs. Phone visits may be replaced by in-clinic visits where relevant, e.g., in subjects going to the dialysis unit for haemodialysis.
- 5. Informed consent must be signed by both subject and investigator before any trial-related procedures are performed.

Clinical Trial Protocol

Protocol No. MC2-25-C1 Vers.3.0 EU/30-Nov-2022

- 6. At-home (diary) assessments must be performed for 8 days leading up to each visit, i.e., from day -7 to day 0 where day 0 = next on-site visit day.
- 7. The WI-NRS must also be reported by the subject at on-site visits
- 8. At all on-site visits, all patient-reported outcome (PRO) assessments should be completed before all other clinical assessments or procedures.
- 9. The trial staff must estimate the % body surface area treated based on the subject's indication of CKD-aP treatment area size on the CKD-aP treatment area diagram.
- 10. Physical exam: A complete physical examination is required at Screening and Week 12 (EoT or Early Termination) visits. An abbreviated physical examination is required at the Baseline visit (and if judged necessary by the investigator) at the FU visit if the FU visit is applicable.

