7.8.1 Haematology and biochemistry

For all subjects, the following tests will be performed at Screening, Baseline, Week 4, and Week 12 or Early Termination. For subjects with ongoing SAEs or related AEs at Week 12, laboratory tests will also be performed at Week 14 (Follow-up) if judged necessary by the investigator. In patients on dialysis, the blood samples must be collected before dialysis:

- Haematology: haemoglobin, haematocrit, red blood cell (RBC) count, mean corpuscular volume (MCV), and white blood cells (WBC) count (basophils, eosinophils, neutrophils, lymphocytes, and monocytes), including differential count and platelet count
- Serum biochemistry: urea, creatinine, albumin, sodium, potassium, chloride, calcium, phosphate, alkaline phosphatase (ALP), aspartate aminotransferase (AST), and alanine aminotransferase (ALT)

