7.13 COVID-19 Considerations

COVID-19 control measures in different countries may impact the ability to adhere to some of the trial procedures described in this protocol. Due to challenges that include, but are not limited to, subject preferences, site closures, travel restrictions, and quarantines, some modifications to trial conduct during the COVID-19 pandemic may be necessary to ensure trial continuity. The following are allowable, as necessary, modifications to trial conduct during the COVID-19 pandemic.

- Prior to a trial visit at the site, the subject may be contacted and may be asked to be screened for potential exposure or infection to COVID-19 per local requirements. If the subject is suspected or known to be infected with COVID-19, the on-site visit may either be re-scheduled or a virtual visit may be performed instead, as applicable.
- If a subject cannot attend the regularly scheduled trial visits in person due to COVID-19 necessitating a limit on in-person contact, the investigator may perform safety and efficacy assessments by phone or video to the extent possible. The investigator may use technology platforms that are considered suitable by the site.
- Source documentation and the eCRF should note that the visit was performed virtually (not face-to-face). If certain trial procedures or assessments cannot be completed per the SoA, the reason for the missed assessment must be noted in the source documentation (e.g., COVID-19) and captured in the protocol deviations documentation.

A detailed assessment of COVID-19-related risk and mitigation measures will be documented in the appropriate trial plans, e.g., trial risk management plan.

Subjects who missed significant WI-NRS assessments due to COVID-19 may be replaced if the total number exceeds 10% of subjects enrolled.

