8.2 Sample size and power considerations

Approximately 108 subjects will be randomized in the trial in 2:1 ratio of MC2-25 cream to MC2-25 vehicle, including an assumption of 10% dropouts. For a two-sided test with a 5% level of significance (expected d=1.5 and s=2.46, d/s=0.61) this sample size will provide adequate power (\geq 80%) to compare mean change in WI-NRS from Baseline to Week 12 between MC2-25 cream and MC2-25 vehicle with 72 and 36 subjects (Spencer 2018).

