3.5 Safety Endpoints

- Frequencies of treatment-emergent adverse events (TEAEs), treatment-emergent serious AEs (TESAEs), treatment-related TEAEs (unlikely related, probably related, and possibly related), TEAEs leading to treatment discontinuation or trial withdrawal, and deaths during the trial for MC2-25 cream compared to MC2-25 vehicle.

- Mean change in vital signs (heart rate (HR), systolic blood pressure (SBP), diastolic blood pressure (DBP), and body temperature (temp)) from Baseline to Week 4, Week 8 and Week 12 for MC2-25 cream compared to MC2-25 vehicle.

Shift in frequencies of clinically significant and not clinically significant vital signs values from Baseline to Week 4, Week 8 and Week 12 for MC2-25 cream compared to MC-25 vehicle.

- Mean change in laboratory assessments (biochemistry and hematology) from Baseline to Week 4 and Week 12 for MC2-25 cream compared to MC2-25 vehicle. Shift in frequencies of normal, abnormal and abnormal clinically significant or not clinically significant laboratory values from Baseline to Week 4, Week 8 and Week 12 for MC2-25 cream

compared to MC-25 vehicle.

- Shifts in physical examination from Baseline to Week 12 by body area will be displayed. Frequencies of normal, abnormal and abnormal clinically significant and abnormal clinically not significant values of physical examination from Baseline to Week 12 for MC2-25 cream compared to MC-25 vehicle.
- Shifts in electrocardiograms (ECGs) from Baseline to Week 4 and Week 12 will be displayed. Frequencies of normal, abnormal and abnormal clinically significant and abnormal clinically not significant values from Baseline to Week 4 and Week 12 for MC2-25 cream compared to MC-25 vehicle.
- Percentage of subjects who missed 1 or more dialysis visits during the Double-blind Treatment Period as recorded on end of trial visit. Not applicable (NA) category will be presented for subjects not on dialysis.

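### SAP 5.2.3 keeps one whole visit per window and leaves a completer's Week 12 visit after Day 92 unassigned; SAP 3.5 plans a Week 8 laboratory shift with no scheduled sample

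*SAP*

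**What the plan says.** SAP 5.2.3 assigns actual visits to analysis visits for efficacy and safety alike. If several fall in one window, "the visit closest to the target day will be used as the protocol visit for that visit window", and a tie goes to the later visit. For the rest, "The other additional visit(s) will not be used in the summaries or analyses"; the same sentence makes an exception for clinically important endpoints, which it does not define. Nothing requires the kept visit to hold the assessment in question. Table 10 sets Week 12 at Days 72 to 92 around target Day 85, and its Week 14 row has no numeric window.

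Other parts of the plan make extra or late visits possible. Protocol Table 3, footnote 2, states: "An unscheduled visit can be conducted to perform any of the postbaseline assessments or procedures included in the SoA". Protocol 7.13 says that, for COVID-19, "the on-site visit may either be re-scheduled or a virtual visit may be performed instead".

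SAP 3.1 ties the weekly diary mean to the eight days ending on a scheduled in-clinic visit and sets it to missing below four entries. SAP 5.2.1 sends missing values to multiple imputation. The nearest-time-point rule in SAP 5.1 is written for subjects who withdraw early.

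On laboratory data, Protocol 7.8.1 says "the following tests will be performed at Screening, Baseline, Week 4, and Week 12 or Early Termination". In SAP 3.5 the mean change in laboratory values is to Weeks 4 and 12, but the shift table covers "clinically significant or not clinically significant laboratory values from Baseline to Week 4, Week 8 and Week 12".

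**The concern.** A rule that chooses whole visits by distance works when every visit carries the same assessments. Here an unscheduled visit may consist of one blood sample or one vital-sign check. If it lies nearer the target day, the scheduled visit leaves the by-visit summaries with everything recorded at it. Safety values are not imputed and the other efficacy endpoints are summarised as observed, so the displaced values simply disappear from those tables.

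The upper bound at Day 92 bears on the primary endpoint. Protocol 6.3 continues treatment until the Week 12 visit, so a completer seen late is still on treatment and may have a full diary. With no analysis visit to hold it, that mean would be imputed although it was observed, and the LOCF analysis would carry an earlier value over it. SAP 5.2.4 makes no adjustment for COVID-affected visits because the endpoints come from diaries. But the diary week is fixed by the visit date, so a moved visit does affect it.

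The Week 8 laboratory shift would describe either nobody or a group sampled outside the schedule.

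**Working it through.** **Inputs.** SAP Table 10 (windows and targets), SAP 3.1 (eight diary days, minimum four), Protocol Table 3 (visit windows, follow-up timing, assessments per visit), Protocol 8.2 (72 and 36 subjects, d = 1.5, s = 2.46, 10% dropout). Days are SAP days: SAP Day 1 is protocol Day 0, so the protocol's Week 12 visit window is Day 85 ± 4, or Days 81 to 89.

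1. *The plan's own figure.* Power = Φ(d / (s·√(1/n₁ + 1/n₂)) − 1.96).
   - With 72 and 36: 1.5 / (2.46 × 0.2041) = 2.987, giving Φ(1.027) = 0.848.
   - After 10% dropout (64.8 and 32.4): 1.5 / (2.46 × 0.2152) = 2.834, giving Φ(0.874) = 0.809.
   - The stated 80% or more is reproduced and is not in dispute.

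2. *Two visits in one window, on-site items.* Suppose the Week 4 visit is on Day 26 with laboratory samples, and an unscheduled visit without samples is on Day 31. Distances to target Day 29 are 3 and 2. Day 31 is kept, and the Day 26 laboratory values leave the Week 4 summaries. At Week 12, with a scheduled visit on Day 82 and an unscheduled one on Day 87, the distances to Day 85 are again 3 and 2. The Day 82 on-site WI-NRS, CGA and CTA are displaced.

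3. *The same Week 12 pair, diary mean.*
   - If 5.2.3 prevails, the eight days are Days 80 to 87. Entries exist for Days 75 to 82, the overlap is Days 80 to 82, and 3 entries is below 4, so the mean is missing.
   - If the anchor in 3.1 prevails, Days 75 to 82 are used, with 8 of 8 entries.
   - Pairing a scheduled visit on Days 81 to 89 with a different day in 72 to 92 gives 9 × 20 = 180 pairs. Under the 5.2.3 reading the other visit is kept in 36. In 10 of these the mean becomes missing; in 26 it rests on 4 to 7 entries. These are counts of day-pairs, not probabilities.

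4. *Upper bound of Week 12.* The window reaches 85 − 72 = 13 days early and 92 − 85 = 7 days late. A Visit 9 on Day 93 with a complete diary for Days 86 to 93 has 8 of 8 entries but lies in no numeric window. Day 93 is 93 − 89 = 4 days past the protocol visit window.

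5. *Follow-up visit.* Visit 10 falls 14 ± 2 days after end of treatment.
   - After Day 85 that is Days 97 to 101; after Day 81, Days 93 to 97. Any extension past Day 92 can meet follow-up data.
   - An overlap is already possible. An early end-of-treatment visit on Days 72 to 78, with follow-up 14 days later on Days 86 to 92, puts both in the Week 12 window. The follow-up visit is nearer (Day 72: 13 against 1) or ties and is later (Day 78: 7 against 7). Visit 10 carries no itch or skin assessment.

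6. *Week 8 laboratory window.* This is Days 44 to 71. On-schedule Week 4 samples end at Day 33 and Week 12 samples start at Day 81. SAP 5.2.3 keeps early-termination safety data at Week 12/EoT. With visits on schedule, only unscheduled samples could fill Week 8. SAP 5.2.3 has a rule for assessments not planned at Week 1, but none for those not planned at Week 8.

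7. *Size per subject.* 1/108 = 0.9% of the full analysis set; 1/36 = 2.8% of the vehicle arm. Assuming 1 to 5 late completers, which no figure in the documents supports or excludes, gives 0.9% to 5/108 = 4.6%.

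**The case against.** A reader might infer that the window rule routinely discards observed Week 12 diary data. The documents do not support that. SAP 3.1 and 3.3 define the diary endpoints by scheduled in-clinic visits, and on a fair reading an unscheduled Day 87 visit cannot take over the diary mean. What stands is that the SAP never says which section governs, and that 3.1 protects neither the on-site and safety values nor a completer seen after Day 92.

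The unequal 13 and 7 days are not in themselves an error. Day 72 simply follows the end of the Week 8 window, and Day 92 already allows 3 days beyond the protocol limit. Nor does the treatment-policy strategy promise that every out-of-window value is used; it concerns intercurrent events. It is also not established that late completers leave the per-protocol set, because SAP section 4 asks for WI-NRS data for Week 12 without saying that it must be the windowed diary mean.

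On safety, a reader might infer that abnormal laboratory values are hidden. They remain in the listings (SAP 5.6.5), clinically significant ones become adverse events (Protocol 7.8), and extra visits may serve the undefined clinically important endpoints. The loss is confined to by-visit summaries and shift tables. The Week 8 entry is most simply read as a drafting slip; that it would display samples taken for cause is conjecture.

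**Conclusion.** Three narrow gaps hold. Selection by whole visit can replace scheduled on-site and safety values with a visit that lacks them, and the diary mean is exposed only if 5.2.3 overrides 3.1. A completer's Week 12 visit on Day 93 or later has no analysis visit, so its observed primary-endpoint value would be imputed. The Week 8 laboratory shift has no scheduled data behind it.

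The size cannot be computed. The documents give no frequency of unscheduled or late visits, and visits at least 4 days past the protocol window should be uncommon. The rule is the same in both blinded arms and no direction of bias is shown. The planned power is not called into question. The point is worth settling before unblinding, because choosing between visits afterwards would be open to knowledge of the results.

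**What to change.** - In SAP 5.2.3, apply the closest-to-target rule separately for each endpoint, only among visits with a non-missing value, preferring the scheduled visit. State that diary weekly means are anchored to the scheduled visit.
- Assign a completer's Visit 9 after Day 92 to Week 12, for example up to Day 98, which matches the 13 days allowed on the early side (85 + 13 = 98). Exclude Visit 10 follow-up data from the Week 12 window explicitly; otherwise off-treatment laboratory or vital-sign values could fill a missing Week 12 value.
- In SAP 3.5, delete Week 8 from the laboratory shift.

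The cost is SAP wording only. The small downside is that a few Week 12 values would come from slightly longer treatment. A shift table to the worst post-baseline value would be an optional addition, not a correction that the documents require.
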